### 6.3 LOST TO FOLLOW-UP

A subject will be considered lost to follow-up if he or she fails to return for 2 scheduled visits and is unable to be contacted by the study site staff.

The following actions must be taken if a subject fails to be available for a required study visit:

- The site will attempt to contact the subject and reschedule the missed visit and counsel the subject on the importance of maintaining the assigned visit schedule and ascertain if the subject wishes to and/or should continue in the study.
- Before a subject is deemed lost to follow-up, the investigator or designee will make every effort to regain contact with the subject (where possible, 3 telephone calls and, if necessary, a certified letter to the subject's last known mailing address or local equivalent methods). These contact attempts should be documented in the subject's medical record or study file.
- Should the subject continue to be unreachable, he or she will be considered to have withdrawn from the study with a primary reason of lost to follow-up.

## 7 STUDY ASSESSMENTS AND PROCEDURES

## 7.1 STUDY ASSESSMENTS

- twice-daily phone calls for the first 4 days post-surgery

At each phone call, the following surveys will be performed:

- Medication Intake Survey
  - Since the last phone call:
    - Which medications have been consumed?
    - How many pills?
- Pain Survey
  - On a scale of 1-10, with 10 being the worst, what is your pain right now?
- Sleep Quality Survey
  - On a scale of 0-5, with 5 being the best, how was your sleep last night?
  - How many hours were you able to sleep before being interrupted by pain?

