## 1 PROTOCOL SUMMARY

### 1.1 SYNOPSIS

Title:	Nerve block with liposomal bupivacaine yields fewer complications and similar pain relief when compared to an interscalene catheter for arthroscopic shoulder surgery: a randomized controlled trial
Study Description:	This is a blinded, randomized controlled trial to compare the control arm (continuous ropivacaine ISC) to the experimental arm (single-injection, brachial plexus nerve block using liposomal bupivacaine) in patients undergoing outpatient arthroscopic shoulder surgery at a single, tertiary academic institution.
Objectives:	

• Compare complication rates

• Compare pain level, dose frequency of prescribed opioid analgesics, consumption of prescribed nonopioid analgesics, quantity and quality of sleep, and overall satisfaction with pain control

• Compare patient-reported outcome measures

Endpoints:	

• Patient reported complications on post-op day 0, 1, 2, 3, and 4

• Visual Analog Scale, prescribed opioid analgesic dose frequency, consumption of prescribed nonopioid analgesics, hours of uninterrupted sleep, subjective quality of sleep (0-10 scale), and pain control overall satisfaction (five-point Likert scale) on post-op day 0, 1, 2, 3, and 4

• Visual Analog Scale, Single Assessment Numeric Evaluation, American Shoulder and Elbow Surgeons Standardized Shoulder Assessment Form, and Penn Shoulder Score at 12 weeks post-op

Study Population:	Patients greater than 19 years of age undergoing outpatient arthroscopic shoulder surgery
Phase:	Not Applicable

Description of Study Intervention:	Patients in the ISC arm will have a 19 gauge Arrow Continuous Nerve Catheter (Teleflex, Wayne, PA, USA) placed with a bolus of 15-20 mL of 0.5% ropivacaine given through the needle prior to threading the catheter. An elastomeric, basal-only, On-Q infusion pump (Avanos Medical, Alpharetta, GA, USA) with 0.2% ropivacaine will be started in the post-anesthesia care unit at 8 mL/hour, and the catheter will be removed by the patient after two days. For patients in the LB arm, 10 mL (133 mg) of liposomal bupivacaine (Pacira BioSciences, Parsippany, NJ, USA) mixed with 7 mL (35 mg) bolus of 0.5% bupivacaine will be injected.
Study Duration:	January 1, 2020 to December 1, 2021
Subject Duration:	3 months

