## 1.2 SCHEDULE OF ACTIVITIES (SOA)

- *Screening/Consent Visit*
- *Randomization Visit*
- *Day of Surgery Visit*
- *Call 1: Evening after surgery (Day 0)*
- *Call 2: Day 1 morning*
- *Call 3: Day 1 evening*
- *Call 4: Day 2 morning*
- *Call 5: Day 2 evening*
- *Call 6: Day 3 morning*
- *Call 7: Day 3 evening*
- *Call 8: Day 4 morning*
- *Call 9: Day 4 evening*

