## 8 STATISTICAL CONSIDERATIONS

### 8.1 STATISTICAL HYPOTHESES

- Primary Efficacy Endpoint(s): Postoperative Pain Scores
- Secondary Efficacy Endpoint(s): Postoperative Oral Morphine Equivalents, Analgesia Satisfaction, Analgesia Complications, Sleep Quality, and Hours of Painless Sleep

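### The sleep questions are set for every call, so the Day 0 sleep-quality answer concerns the night before the block; four post-operative nights must fill five endpoint days, and the quality scale is 0-5 in 7.1 but 0-10 in 1.1

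*Combined protocol and SAP*

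**What the plan says.** - **Instrument (7.1).** The sleep survey has two items. The quality item reads "On a scale of 0-5, with 5 being the best, how was your sleep last night". The second asks for the hours slept before pain interrupted sleep, and it names no night.
- **Timing (7.1, 1.2, 3.1).** Section 7.1 states "At each phone call, the following surveys will be performed", with no morning-only limit on sleep. Section 3.1 agrees, putting sleep among the data collected by phone every 12 hours. Section 1.2 opens the calls with "Call 1: Evening after surgery (Day 0", then "Call 2: Day 1 morning" and "Call 3: Day 1 evening". It continues with a morning and an evening call each day up to Call 9 on the evening of Day 4. Section 7.1 describes "twice-daily phone calls for the first 4 days post-surgery", which alone would make eight calls; the Day 0 evening call makes nine.
- **Endpoint (1.1).** The synopsis lists hours of uninterrupted sleep and "subjective quality of sleep (0-10 scale") among the endpoints for post-operative days 0, 1, 2, 3 and 4.
- **Status and analysis (8.1, 8.3).** Section 8.1 includes "Sleep Quality, and Hours of Painless Sleep" among the secondary efficacy endpoints. Section 8.3 compares duration and quality of sleep by Mann-Whitney U tests. It does not say which night belongs to which day, which of two answers about one night is used, or how a 0-5 answer relates to a 0-10 endpoint.

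**The concern.** A recall question about the previous night works at a morning call. At the Day 0 evening call it reaches back before the block, when the arms cannot yet differ because of treatment. At each later evening call it asks again about a night already reported that morning. The stated collection rule and the stated endpoint days therefore do not fit together.

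At stake is what the reported sleep results mean. A Day 0 result could be read as an early treatment effect, or as evidence of no difference, when it is a baseline comparison. Two analysts following the same text could assign the same answer to different days or choose different answers for the same night. Because the scale differs between sections, a reader cannot tell whether a score of 5 is the best possible or the midpoint.

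**Working it through.** The plan gives no figure for sleep, so there is none to reproduce. The check maps each call in section 1.2 to the night its quality answer describes.

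| Calls | Night described | Label by call day | Label by day the night begins |
|---|---|---|---|
| 1 (Day 0 evening) | Night before surgery | Day 0 | Before Day 0 |
| 2, 3 (Day 1) | Post-operative night 1 | Day 1 | Day 0 |
| 4, 5 (Day 2) | Post-operative night 2 | Day 2 | Day 1 |
| 6, 7 (Day 3) | Post-operative night 3 | Day 3 | Day 2 |
| 8, 9 (Day 4) | Post-operative night 4 | Day 4 | Day 3 |
| No Day 5 call | Post-operative night 5 | none | Day 4 (empty) |

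**Counts.** 1 + 4 × 2 = 9 answers covering 5 nights, of which 4 are post-operative. One of 9 answers (1/9 = 11%), or one of 5 call-day values (1/5 = 20%), precedes treatment. The other 8 answers form four pairs, so 4 of 9 (44%) are second reports of a night already described.

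**Labelling.** By call day, Day 0 is filled with a pre-treatment value. By the day the night begins, Day 0 is genuinely post-operative (from Calls 2 and 3) but Day 4 is empty. Under neither do five endpoint days each have a post-operative night.

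**Scale.** A 0-5 item has 6 whole-number levels and a 0-10 item has 11. No conversion is given.

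**Why a rule for the records is needed (illustration only).** The plan does not say that records are averaged or pooled. The figures below assume that they are, with a normal approximation and a two-sided 0.05 test.

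- *Averaging in the pre-operative night.* Assume an equal effect on every post-operative night, an unchanged standard error, and 80% power without that night. Let f be the post-operative share of the average. Power = Φ(f × (1.96 + 0.84) − 1.96).
  - f = 8/9 (nine calls): about 70%.
  - f = 4/5 (five call-day values): about 61%.
- *Treating two reports of one night as independent.* With correlation ρ between them, the actual two-sided error is 2 × (1 − Φ(1.96/√(1 + ρ))).
  - ρ = 0.5: 0.110.
  - ρ = 0.8: 0.144.
  - ρ = 1.0: 0.166.

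The 80% is borrowed for illustration; section 8.2 powers the trial on complication rates, not sleep.

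**After the change.** Calls 2, 4, 6 and 8 alone give 4 answers, one for each post-operative night, and none for the night before surgery.

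**The case against.** The strongest reply is that this is a missing analysis rule rather than spoiled data, and much of that stands.

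- A reader might infer that each night is counted twice, or that repeated answers pass as independent observations. The documents do not support this. Section 8.3 names a Mann-Whitney test and no pooling; a test per call or per day uses one value per patient.
- A reader might infer that the treatment effect is diluted by 11%. That needs the nine calls to be averaged and a constant effect across nights, and neither is in the plan.
- A reader might infer that the timing fault cannot be repaired. It can: answers belong to labelled calls, so selecting Calls 2, 4, 6 and 8 recovers the wanted nights.
- The Mann-Whitney test depends only on ranks, so doubling every 0-5 score leaves it unchanged. If one scale was used throughout, the mismatch costs granularity and a clear meaning for reported values, not the validity of the test.
- Labelling nights by the day they begin makes Day 0 post-operative. That is true, but it moves the gap to Day 4.
- Section 7.1 may be only an outline, since it omits the complication and satisfaction questions that section 1.1 requires. However, section 3.1 separately puts sleep at 12-hourly calls.
- Sections 3.1 and 8.3 are partly in the past tense, and section 1.1 ends the study in December 2021. Changing the call script may be too late, but an analysis and reporting rule would not be.

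What survives is the mismatch between four nights and five days, the pre-treatment Day 0 value under call-day labelling, the absent rule for repeated answers, and the contradictory scale.

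**Conclusion.** The point holds in a limited form. For sleep quality, the stated rules give four post-operative nights for five endpoint days. Labelled by call day, the Day 0 comparison tests a pre-treatment value. Labelled by the start of the night, Day 4 cannot be filled. Each of the four nights has two answers and no rule for choosing between them. This rests on reading 7.1 and 1.2 as written, with the sleep survey at all nine calls.

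The 0-5 against 0-10 conflict is explicit and needs no inference. The documents do not show which scale was administered, so neither can be called the correct one.

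Two limits apply. The power and error figures above are conditional on averaging or pooling and are not properties of this plan. The hours item states no recall period, so the same fault is likely there but not explicit; a reader might extend the finding to both items, but the text supports it only for quality.

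Sleep is a secondary endpoint in 8.1 and does not enter the power statement in 8.2. The point affects the interpretation of the sleep results, not the sample size or the primary comparison. It should be corrected because the correction is precise and nearly free.

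**What to change.** 1. In 1.1, define both sleep endpoints as post-operative nights 1 to 4 in place of days 0 to 4.
2. In 7.1 and 8.3, take each night from the morning call (Calls 2, 4, 6 and 8 for nights 1 to 4), using the same-day evening answer only if the morning call was missed.
3. Exclude the Call 1 answer as an outcome; if recorded, keep it as a baseline value.
4. Give the hours item the same recall period as the quality item.
5. State one sleep-quality scale in 1.1 and 7.1. It must be the scale that was actually administered.

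If the calls are already complete, apply items 1 to 3 as an analysis and reporting rule, report the scale used, and say that the hours item had no stated recall period.

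The cost is wording plus a selection rule in the analysis. The real loss is that the sleep endpoint becomes four nights instead of five days. Keeping a fifth post-operative night would need a further call on the morning of Day 5, which is possible only if data collection is still open.

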## 7.2 ADVERSE EVENTS AND SERIOUS ADVERSE EVENTS

### 7.2.1 DEFINITION OF ADVERSE EVENTS (AE)

Adverse event means any untoward medical occurrence associated with the use of an intervention in humans, whether or not considered intervention-related (21 CFR 312.32 (a)).

### 7.2.2 DEFINITION OF SERIOUS ADVERSE EVENTS (SAE)

An adverse event (AE) is considered “serious” if, in the view of either the investigator or sponsor, it results in any of the following outcomes:

- Death
- A life-threatening adverse event (of note, the term “life-threatening” refers to an event in which the subject was at risk of death at the time of the event, rather than to an event which hypothetically might have caused death if it were more severe)
- inpatient hospitalization or prolongation of existing hospitalization
- a persistent or significant incapacity or substantial disruption of the ability to conduct normal life functions
- or a congenital anomaly/birth defect.

Important medical events that may not result in death, be life-threatening, or require hospitalization may be considered serious when, based upon appropriate medical judgment, they may jeopardize the subject and may require medical or surgical intervention to prevent one of the outcomes listed in this definition. Examples of such medical events include allergic bronchospasm requiring intensive treatment in an emergency room or at home, blood dyscrasias or convulsions that do not result in inpatient hospitalization, or the development of drug dependency or drug abuse.

### 7.2.3 CLASSIFICATION OF AN ADVERSE EVENT

#### 7.2.3.1 SEVERITY OF EVENT

For adverse events (AEs), the following guidelines will be used to describe severity:

- **Mild** – Events require minimal or no treatment and do not interfere with the subject's daily activities.
- **Moderate** – Events result in a low level of inconvenience or concern with the therapeutic measures. Moderate events may cause some interference with functioning.
- **Severe** – Events interrupt a subject's usual daily activity and may require systemic drug therapy or other treatment. Severe events are usually potentially life-threatening or incapacitating. Of note, the term "severe" does not necessarily equate to "serious."

#### 7.2.3.2 RELATIONSHIP TO STUDY INTERVENTION

All adverse events (AEs) must have their relationship to study intervention assessed by the clinician who examines and evaluates the subject based on temporal relationship and his/her clinical judgment. The degree of certainty about causality will be graded using the categories below. In a clinical trial, the study product must always be suspect.

- **Related** – The AE is known to occur with the study intervention, there is a reasonable possibility that the study intervention caused the AE, or there is a temporal relationship between the study intervention and event. Reasonable possibility means that there is evidence to suggest a causal relationship between the study intervention and the AE.
- **Not Related** – There is not a reasonable possibility that the administration of the study intervention caused the event, there is no temporal relationship between the study intervention and event onset, or an alternate etiology has been established.

#### 7.2.3.3 EXPECTEDNESS

The Principal Investigator will be responsible for determining whether an adverse event (AE) is expected or unexpected. An AE will be considered unexpected if the nature, severity, or frequency of the event is not consistent with the risk information previously described for the study intervention.

#### 7.2.4 TIME PERIOD AND FREQUENCY FOR EVENT ASSESSMENT AND FOLLOW-UP

The occurrence of an adverse event (AE) or serious adverse event (SAE) may come to the attention of study personnel during study visits and interviews of a study subject presenting for medical care, or upon review by a study monitor.

All AEs including local and systemic reactions not meeting the criteria for SAEs will be captured on the appropriate case report form (CRF). Information to be collected includes event description, time of onset, clinician's assessment of severity, relationship to study product (assessed only by those with the training and authority to make a diagnosis), and time of resolution/stabilization of the event. All AEs occurring while on study must be documented appropriately regardless of relationship. All AEs will be followed to adequate resolution.

Any medical condition that is present at the time that the subject is screened will be considered as baseline and not reported as an AE. However, if the study subject's condition deteriorates at any time during the study, it will be recorded as an AE.

Changes in the severity of an AE will be documented to allow an assessment of the duration of the event at each level of severity to be performed. AEs characterized as intermittent require documentation of onset and duration of each episode.

The Study Coordinator will record all reportable events with start dates occurring any time after informed consent is obtained until 7 (for non-serious AEs) or 30 days (for SAEs) after the last day of study participation. At each study visit, the Study Coordinator will inquire about the occurrence of AE/SAEs since the last visit. Events will be followed for outcome information until resolution or stabilization.

#### 7.2.5 ADVERSE AND SERIOUS ADVERSE EVENT REPORTING

All serious adverse events must be reported to the IRB according to regulatory requirements. The Principal Investigator will immediately report to the sponsor any serious adverse event, whether or not considered study intervention related, including those listed in the protocol or package insert and must include an assessment of whether there is a reasonable possibility that the study intervention caused the event. Study endpoints that are serious adverse events (e.g., all-cause mortality) must be reported in accordance with the protocol unless there is evidence suggesting a causal relationship between the study intervention and the event (e.g., death from anaphylaxis). In that case, the investigator must immediately report the event to the sponsor.

All serious adverse events (SAEs) will be followed until satisfactory resolution or until the Principal Investigator deems the event to be chronic or the subject is stable. Other supporting documentation of the event may be requested and should be provided as soon as possible.

### 7.3 UNANTICIPATED PROBLEMS

#### 7.3.1 DEFINITION OF UNANTICIPATED PROBLEMS (UP)

The Office for Human Research Protections (OHRP) considers unanticipated problems involving risks to subjects or others to include, in general, any incident, experience, or outcome that meets all of the following criteria:

- Unexpected in terms of nature, severity, or frequency given (a) the research procedures that are described in the protocol-related documents, such as the Institutional Review Board (IRB)-approved research protocol and informed consent document; and (b) the characteristics of the subject population being studied;
- Related or possibly related to participation in the research (“possibly related” means there is a reasonable possibility that the incident, experience, or outcome may have been caused by the procedures involved in the research); and
- Suggests that the research places subjects or others at a greater risk of harm (including physical, psychological, economic, or social harm) than was previously known or recognized.

#### 7.3.2 UNANTICIPATED PROBLEM REPORTING

The investigator will report unanticipated problems (UPs) to the reviewing Institutional Review Board (IRB). The UP report will include the following information:

- Protocol identifying information: protocol title and number, PI’s name, and the IRB project number;
- A detailed description of the event, incident, experience, or outcome;
- An explanation of the basis for determining that the event, incident, experience, or outcome represents an UP;

- A description of any changes to the protocol or other corrective actions that have been taken or are proposed in response to the UP.

To satisfy the requirement for prompt reporting, UPs will be reported using the following timeline:

- UPs that are serious adverse events (SAEs) will be reported to the IRB within 10 working days of the investigator becoming aware of the event.
- Any other UP will be reported to the IRB within 10 working days of the investigator becoming aware of the problem.

## 8 STATISTICAL CONSIDERATIONS

### 8.1 STATISTICAL HYPOTHESES

- Primary Efficacy Endpoint(s): Postoperative Pain Scores
- Secondary Efficacy Endpoint(s): Postoperative Oral Morphine Equivalents, Analgesia Satisfaction, Analgesia Complications, Sleep Quality, and Hours of Painless Sleep

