## 3 STUDY DESIGN

### 3.1 OVERALL DESIGN

Patients undergoing arthroscopic shoulder surgery were prospectively assessed after randomization into either ropivacaine ISC or single-injection liposomal bupivacaine brachial plexus nerve block (LB) arms. All patients were

discharged with 5 analgesics (acetaminophen, methocarbamol, gabapentin, acetylsalicylic acid, and oxycodone) for as-needed pain relief. Preoperatively, patient demographics and baseline Visual Analog Scale, Single Assessment Numeric Evaluation, American Shoulder and Elbow Surgeons, and Penn Shoulder Scores were obtained. For the first four days postoperatively, complication rates (nausea, dyspnea, anesthetic site discomfort and/or irritation and/or leakage, and self-reported concerns and complications), pain, medication usage, and sleep data were assessed by phone survey every 12 hours. The primary outcome was overall complication rate. At 12 weeks postoperatively, Visual Analog Scale, Single Assessment Numeric Evaluation, American Shoulder and Elbow Surgeons, and Penn scores were reassessed. Outcome scores were compared with Mann-Whitney U tests, and demographics were compared with chi-squared tests. Significance was set at  $P < .05$ .

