### 8.2 SAMPLE SIZE DETERMINATION

A power analysis was conducted at 0.8 with an alpha of 0.05, using liposomal bupivacaine and ISC complication rates calculated from prior literature.

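### Sections 3.1 and 8.1 name different primary endpoints, the power statement in 8.2 covers only one of them, and nothing in the reviewed text says which section governs

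*Combined protocol and SAP*

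**What the plan says.** Four places in the combined protocol and SAP bear on which endpoint is primary.

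- **Section 3.1 (Overall Design):** "The primary outcome was overall complication rate". The statement is singular and unqualified.
- **Section 8.1 (Statistical Hypotheses):** "Primary Efficacy Endpoint(s): Postoperative Pain Scores". Its next line reads "Secondary Efficacy Endpoint(s): Postoperative Oral Morphine Equivalents, Analgesia Satisfaction, Analgesia Complications", followed by two sleep measures. Complications are therefore expressly secondary here.
- **Section 8.2 (Sample Size Determination):** power 0.8 and alpha 0.05, "using liposomal bupivacaine and ISC complication rates calculated from prior literature". It gives no rates and no sample size, and does not mention pain.
- **Section 1.1 (Synopsis):** complications head both the objectives and the endpoints ("Patient reported complications on post-op day 0, 1, 2, 3, and 4"), with pain in the second bullet. Nothing is labelled primary.

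Section 8.3 (Statistical Analyses) assigns Mann-Whitney U tests to pain and chi-squared tests to six perioperative complications, all at P < .05, again without ranking.

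**The concern.** Both statements cannot hold, and the choice has consequences. The trial's title claims fewer complications and similar pain relief, so one candidate primary is said to show a difference and the other similarity. Which of these is the confirmatory result depends on which section governs.

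Three things are at stake:

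- **Error rate.** If either endpoint may be called primary once results are known, testing at P < .05 no longer limits the chance of a false primary claim to 5%.
- **Power.** If 8.1 governs, the 0.8 describes a secondary endpoint and no power is stated for the primary.
- **Definition of the test.** Whichever section governs, 8.3 does not identify one test as the primary analysis.

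**Working it through.** The finding rests on the text. There is no stated sample size or effect size to reproduce. The arithmetic below shows only why the choice matters.

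**1. The sections side by side**

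| Section | Complications | Pain |
|---|---|---|
| 1.1 | listed first, unranked | listed second, unranked |
| 3.1 | primary | collected, not primary |
| 8.1 | secondary efficacy | primary efficacy |
| 8.2 | basis of the power | not mentioned |
| 8.3 | six separate chi-squared tests | Mann-Whitney U, no time point |

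Sections 3.1 and 8.2 and the order in 1.1 lean towards complications. Only 8.1 names pain. No section says that it overrides another.

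**2. Is there a single primary test under either reading?**

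- *Complications.* Section 8.3 lists nausea, dyspnea, site discomfort, irritation, leakage and self-reported complications, which makes six tests. It lists no test of the overall rate that 3.1 calls primary.
- *Pain.* Section 1.2 schedules nine calls and 7.1 asks for pain at each. Section 8.3 does not say which call, or what summary of them, is tested.

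**3. Error rate (illustration)**

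Assumptions: either endpoint can be claimed, one two-sided test of each at 0.05, both nulls true. The documents state neither the sidedness nor the correlation.

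- Upper bound, no distributional assumption: 0.05 + 0.05 = 0.10.
- Independent tests: 1 − 0.95² = 0.0975.
- Fully dependent tests: 0.05.
- Bivariate normal, 1 − P(|Z₁| ≤ 1.96 and |Z₂| ≤ 1.96): 0.0964, 0.0907 and 0.0835 at correlations 0.2, 0.5 and 0.7.
- The same with one-sided tests: 0.095, 0.088 and 0.080, so sidedness matters little.

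More than one test per endpoint can raise these figures. For the six complication tests alone, independence would give 1 − 0.95⁶ = 0.265. The components need not be independent, so this is only a marker of direction.

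**4. Does power for complications carry over to pain? (illustration)**

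All rates and the pain effect here are assumed: 1:1 allocation, two-sided 0.05, power 0.8.

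Per-arm n = [1.96·√(2p̄(1−p̄)) + 0.842·√(p₁(1−p₁) + p₂(1−p₂))]² / (p₁−p₂)². Power for a pain difference of 0.5 SD = Φ(0.5·√(n/2) − 1.96), by normal approximation.

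| Assumed complication rates | n per arm | Power for pain at 0.5 SD |
|---|---|---|
| 40% vs 10% | 32 | Φ(2.00 − 1.96) = 0.52 |
| 30% vs 10% | 62 | Φ(2.78 − 1.96) = 0.80 |
| 40% vs 20% | 82 | Φ(3.20 − 1.96) = 0.89 |

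A trial with 0.8 power for complications can have anything from about a half to nearly 0.9 for this one pain effect. The 0.8 in 8.2 therefore says nothing definite about pain.

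**The case against.** **Section 8.1 ranks efficacy only, and 3.1 names the overall primary.** This would reconcile the two if complications were treated as safety. It fails because 8.1 itself lists complications as a secondary *efficacy* endpoint.

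**The balance of the text already points to complications.** This is the strongest objection, and it stands as a statement of weight. It does not resolve the conflict. Section 8.2 describes how the trial was sized without naming a primary, and the synopsis order carries no label. The section headed as the statistical hypotheses says the opposite.

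**The error figures do not describe this trial.** This also stands. No passage says that either endpoint may be claimed, and neither has a single defined test. The 5% to 10% range is neither an estimate nor a ceiling for the plan as written.

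**A reader might infer that the primary was switched after the data were seen.** Parts of the document were written late: the title states the result, 8.3 reports the outcome of a normality test, and a reference was accessed on March 4, 2022, after the December 1, 2021 end date. These facts date those parts only. They do not date 8.1 and are not evidence of switching. The front pages were not available for review and may carry a version history.

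**A reader might also take 7.1 as evidence that pain was the real primary.** Section 7.1 says "At each phone call, the following surveys will be performed" and lists medication, pain and sleep only, whereas 3.1 says "self-reported concerns and complications), pain, medication usage, and sleep data were assessed by phone survey every 12 hours". Section 7.2.4 adds "At each study visit, the Study Coordinator will inquire about the occurrence of AE/SAEs since the last visit", which neither mentions nor excludes calls. But 7.1 also omits satisfaction, which 1.1 and 8.1 both list as an endpoint, so it looks like an incomplete list. The mismatch is a separate data-collection point and shows nothing about priority.

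**Conclusion.** The contradiction between 3.1 and 8.1 is real, and the reviewed text does not resolve it. The weight of the text favours complications without deciding the question. Under 8.1 the only stated power belongs to a secondary endpoint; under either section the primary test is undefined. The 5% error rate is unprotected if both endpoints remain claimable. The size of that problem cannot be derived from the documents, and the illustrative range holds only under the assumptions stated with it. The conclusion is confined to the text available and alleges no change of endpoint. The conflict must be resolved before either result is presented as confirmatory.

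**What to change.** Take the primary from the last IRB-approved version in force before any outcome data were available. The earliest version is the wrong reference, because the Statement of Compliance provides for IRB-approved amendments, and a change made before outcomes were seen would be legitimate. Disclose any such change. Align 3.1, 8.1 and 8.2 through a dated, labelled correction, since silent rewording would hide the discrepancy.

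- **If that version says complications:** amend 8.1 to make the overall complication rate over days 0 to 4 primary and pain secondary. Add to 8.3 one chi-squared test of the overall rate, with the six components as secondary. Label the composite definition post hoc if that version does not define it.
- **If it says pain:** correct 3.1. Use the time point or summary given in that version, labelled post hoc if there is none. State that the 0.8 power applies only to the secondary complication endpoint.
- **If no dated version settles it:** say so, and present neither endpoint as confirmatory.

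Separately, reconcile the call surveys in 7.1 with the statement in 3.1 that complications were assessed by phone every 12 hours.

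The cost is retrieval of the dated version, edits to a few sections and one defined primary test. No new data are needed, provided the complication data described in 3.1 exist. One endpoint loses its primary label, or both lose confirmatory status if no record exists.
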